Safety Assessments	
Safety monitoring will begin when patient signs the informed consent form and continues through the end-of-study visit. All AEs and SAEs, whether reported by the patient/caregiver or noted by authorized study personnel, will be recorded in the patient's medical record and on the appropriate AE/SAE electronic case report form (eCRF).
 
As for SAEs, AESIs have to be reported to the sponsor within 24 hours after learning of the event.
 
An SAE is any AE that meets any of the following criteria:
 
- Fatal (i.e., the AE actually causes or leads to death).- Life-threatening (i.e., the AE, in the view of the investigator, places the patient at immediate risk of death). This does not include any AE that, had it occurred in a more severe form or was allowed to continue, might have caused death.- Requires or prolongs in-patient hospitalization.- Results in persistent or significant disability/incapacity (i.e., the AE results in substantial disruption of the patient's ability to conduct normal life functions).- Congenital anomaly/birth defect in a neonate/infant born to a mother exposed to study drug(s).- Significant medical event in the investigator's judgment (e.g., may jeopardize the patient's safety or may require medical/surgical intervention to prevent one of the outcomes listed above). 
AESI includes:
 
- Electrolyte imbalance: hypokalemia (K^+ level <3.4 mEq/L), hyperkalemia (>5.0 mEq/L), hyponatremia (Na^+ level <135 mEq/L), hypochloremia (Cl^- level <97 mEq/L).

	
 - Thrombocytopenia is defined as meeting one or both criteria: 
 o Platelet count below $150 \times 10^9/L$ (or 150,000 platelets per microliter [mcL]) o Platelet count drop of $\geq 50\%$ compared to baseline - Drug-induced liver injury (DILI). - Dehydration and orthostasis (defined by a fall in systolic blood pressure over 20 mm Hg or a fall in diastolic pressure over 10 mm Hg within 3 minutes of standing). 
The progression from the first cohort to the second will be contingent upon DSMB review and agreement with the sponsor. The information to be reviewed will correspond to the safety and tolerability data from the first dose cohort (8 patients) who finish 2 weeks of treatment and 2 weeks of follow-up. The DSMB members will be independent from the study team.
																		

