5.3.1 ADVERSE EVENT REPORTING PERIOD

Investigators will seek information on AEs at each patient contact. All AEs, whether reported by the patient or the caregiver or noted by study personnel, will be recorded in the patient's medical record. AEs will then be reported on the AE eCRF page as follows:

After informed consent has been obtained but prior to initiation of study drug(s), only SAEs caused by a protocol-mandated intervention should be reported (e.g., SAE related to invasive procedures such as biopsies).

After initiation of study drug(s), all AEs, regardless of relationship to study drug(s), will be reported until the follow-up visit (i.e., 2 weeks after the last dose of study drug[s]).

At the end of the 2-week follow-up period, investigators should report any deaths, SAEs, or other AEs of concern that are believed to be related to prior treatment with study drug(s) (see [Section 5.6](#)).

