1.2 Study Procedures

The study includes assessments at screening (Days -14 to -1), treatment period (Days 1 to 14), and the follow-up visits (Days 16-18 (optional) and Day 28).

Screening Period (Visit 1 - Day -14 to Day -1)

Patients will be screened for study eligibility within 14 days prior to treatment (Days -14 to -1). The following screening procedures will be performed:

- Sign an Informed Consent Form (ICF) before any of the study related procedures are performed
- Eligibility criteria including all inclusion and exclusion criteria
- Record demographics (including age, gender, height, weight, etc.)
- Record medical history including history of substance use
- Record previous and concomitant medications and therapies
- Measure vital signs (temperature, heart rate (HR), and respiratory rate)
- Orthostatic blood pressure (BP) and HR
- Perform physical examination

- Perform blood laboratory tests (serology, blood chemistry, hematology, and coagulation)
- Perform urinalysis laboratory test
- Perform 12-lead ECG
- Perform urine pregnancy test for women of childbearing potential
- Perform SARS-CoV-2 Test
- Perform alcohol urine test/substance abuse urine test
- Adverse event (AE) assessment and recording
- Perform study-specific assessments: (Suicidality (Columbia Suicide Severity Rating Scale [C-SSRS] or Columbia Classification Algorithm for Suicide Assessment [C-CASA]), Aberrant Behavior Checklist- Second Edition – Community (ABC-C), Social Responsiveness Scale, Second Edition (SRS-2), and Stanford Binet Intelligence Scales, Fifth Edition- Abbreviated Battery IQ (SB5 ABIQ), Ohio Autism Clinical Impression Scale -Severity (OACIS-Severity),  Test of Attentional Performance for Children (KiTAP), Children Sleep habit Questionnaire (CSHQ), Clinical Global Impressions – Severity (CGI-S) Scale
 - C-SSRS, OACIS- Severity, NIH-CTB, KiTAP, CSHQ and CGI-S are collected at Screening for only those patients enrolled under Version 4 or subsequent versions of the protocol

Treatment Period (Day 1 to Day 14)

The following procedures will be performed during the treatment period (visits at Day 1, Day 7 & Day 14):

Visit 2 - Day 1

- Randomization
- Physical examination
- Vital Signs (pre- and post-dose): including temperature, HR, respiratory rate, and BP
- Orthostatic BP assessment (pre- and post-dose)
- ECG-12 lead (pre- and post-dose)
- Substance abuse test (urine)

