4.2 Analysis of Safety Variables

Adverse Events

Prior to analysis, all AEs will be recorded and classified on the basis of the Medical Dictionary for Regulatory Activities (MedDRA®) terminology. The number and proportion of patients with at least one AE will be summarized by system organ class (SOC) and by preferred term (PT) within SOC for each treatment group.

Similar tables will be provided to display the number and proportion of patients with at least one treatment-related AE, at least one treatment-related AE that led to study treatment discontinuation, at least one serious AE (SAE), at least one treatment-related SAE, at least one treatment-related SAE that led to study treatment discontinuation, at least one AE of special interest (AESI), and at least one AESI that led to study treatment discontinuation by SOC and by PT within SOC. For the purposes of this study, a treatment-related AE is any AE with a relationship to study drug of 'Related'.

In addition, tables will be constructed to summarize AEs by relationship to study drug and by severity.

A separate AE summary table will be constructed to display the number of patients with at least one AE, the number of patients with at least one treatment-related AE, the number of patients with at least one treatment-related AE that led to study treatment discontinuation, the maximum severity of AE by patient, the highest relationship of AE to treatment, the number of patients experiencing at least one SAE, the number of patients with at least one treatment-related SAE, the number of patients with at least one treatment-related SAE that led to study treatment discontinuation, the maximum severity of SAE by patient, the highest relationship of SAE to treatment, the number of patients with at least one AESI, the number of patients with at least one AESI that led to study treatment discontinuation, and the number of deaths.

All AEs will be provided in data listings as shown in Appendix B. AEs having an end date prior to signing the informed consent for this study will not be displayed in the AE data listings.

Vital Signs

The vital signs parameters of interest include temperature, respiratory rate, and orthostatic blood pressure and orthostatic heart rate.

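### The AE tables have no onset-after-first-dose condition, so any AE captured between consent and first dose can be counted as incidence under STP1 or placebo

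*SAP*

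**What the plan says.** **Counting rule.** SAP 4.2, Adverse Events, says: "The number and proportion of patients with at least one AE will be summarized by system organ class (SOC") and by preferred term, for each treatment group. Tables for SAEs, AESIs, relationship and severity follow the same pattern. Neither the text nor the shells for Tables 4-14 give an onset condition or define a treatment-emergent AE. The Safety population (SAP 2.2) selects patients who were dosed. It does not select events that followed dosing.

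**Date rule.** The one date rule on AEs in SAP 4.2 is that "AEs having an end date prior to signing the informed consent" are left out of the AE listings. It uses the end date, is anchored to consent, and concerns the listings only.

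**Capture before dosing.** The documents give two answers.
- Protocol Synopsis, Safety Assessments: "Safety monitoring will begin when patient signs the informed consent form and continues through the end-of-study visit". All AEs and SAEs are to go in the medical record and "on the appropriate AE/SAE electronic case report form (eCRF").
- Protocol 5.3.1: AEs go in the medical record, but on the AE eCRF page, after consent and before study drug, "only SAEs caused by a protocol-mandated intervention should be reported". The full rule starts later: "After initiation of study drug(s), all AEs, regardless of relationship to study drug(s), will be reported until the follow-up visit".

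Protocol 4.6.2 and Appendix 1 also list AEs at Screening, and SAP 1.2 includes "Adverse event (AE) assessment and recording" among the screening procedures.

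**The concern.** The AE tables are meant to show what happened under STP1 and under placebo. With no onset condition, an event that began before the first dose is counted under the treatment received afterwards. That raises the printed incidence in every group. If the pre-dose rate is similar across groups, it also pulls the active and placebo figures together.

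The groups are very small: up to 6 active patients per dose level, up to 4 on pooled placebo, and possibly only 3 at the highest dose. A single misplaced event is visible in the result. Vital signs and ECG have an explicit pre-dose Day 1 baseline in SAP 4.2; AEs have no equivalent.

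**Working it through.** **The plan's own figure.** The only calculable figure nearby is enrolment: 16 evaluable patients with about 20% dropout gives 16 / (1 - 0.20) = 20, as stated in SAP 1.3. It reproduces, and this point does not change it.

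**Does anything in the SAP remove a pre-dose AE from the tables?** Take an AE that starts after consent and before first dose, in a patient who is then dosed.
1. The patient is in the Safety population, so the event is eligible.
2. It did not end before consent, so the listing rule does not touch it. That rule would not reach the tables in any case.
3. The shells carry no onset footnote.

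If it is in the dataset, it is counted.

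**Which tables?** Tables 6, 7, 9 and 10 require the rating Related. Protocol 5.3.4 bases causality partly on timing, so a pre-dose event should be rated Not related and stay out. Table 12, like 7 and 10, needs an event that led to drug discontinuation, which is unlikely for a purely pre-dose event. That leaves Tables 4, 5, 8, 11, 13 and 14.

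**Weight of one patient** (100/n points, for a patient whose only AE was pre-dose):
- n = 6, one active group at full size: 16.7
- n = 4, pooled placebo at full size: 25.0
- n = 3, the stated minimum at the highest dose: 33.3

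**Expected inflation.** Inputs: 28 days on study (2 weeks of treatment plus 2 of follow-up) and up to 14 days of screening (SAP 1.1). Assumptions not in the documents: a constant background AE rate, every pre-dose AE entered on the eCRF, and the background incidences themselves. With p the incidence over 28 days and s the pre-dose days, the tabulated incidence is 1 - (1 - p)^((28 + s)/28).

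| Assumed p | s = 7 | s = 14 |
|---|---|---|
| 10% | 12.3% | 14.6% |
| 20% | 24.3% | 28.4% |
| 30% | 36.0% | 41.4% |
| 50% | 58.0% | 64.6% |

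For example, 1 - 0.7^(42/28) = 1 - 0.586 = 0.414.

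**Dilution.** If the pre-dose probability q is equal across groups and independent of later events, the difference between groups is multiplied by (1 - q), where q = 1 - (1 - p)^(14/28). For p = 20%, 30% and 50%, q = 10.6%, 16.3% and 29.3%.

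**Lower end.** If sites follow Protocol 5.3.1, only SAEs caused by a protocol-mandated intervention can enter before dosing, and the inflation is close to zero.

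**The case against.** The strongest reply is that Protocol 5.3.1 is the section dedicated to the reporting period, and it keeps almost all pre-dose AEs off the eCRF from which the tables are built. The Screening entries in Appendix 1 and SAP 1.2 can be read consistently with it, since 5.3.1 has AEs sought at every contact but reported on the eCRF under a narrower rule. Only the Synopsis plainly conflicts. In addition, conditions present at screening go to medical history and become AEs only on worsening (Protocol 5.3.5.8). The study is descriptive, with no test of active against placebo. Data Listing 3 shows treatment start and AE start dates together, so a reader can pick out a pre-dose event by hand.

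Most of this stands, and it limits the size of the problem. It does not remove it. The Synopsis conflict is real, and the primary safety tables should not depend on which instruction the site followed. Even under 5.3.1, a procedure-caused SAE before dosing would be tabulated under STP1 or placebo. Protocol 5.3.5.8 does not cover an event that arises between the screening visit and Day 1. A listing that lets a reader find the event does not correct the table.

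A reader might also infer that Cohort 1 patients who enter Cohort 2 will have first-course AEs counted twice. The documents give this little support. Re-entry requires no safety concern and a drug washout, with a new patient ID and new CRFs (SAP 1.1). If such patients are screened afresh, an AE still ongoing falls under 5.3.5.8.

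**Conclusion.** The gap is established: as written, the SAP counts any captured pre-dose AE as incidence under the treatment group, with Tables 4, 5, 8, 11, 13 and 14 mainly exposed. Its numerical effect is not established. It runs from near zero, if 5.3.1 governs the eCRF, up to 20%, 30% or 50% being tabulated as 28%, 41% or 65%. The upper figures need full capture, a constant rate and a full 14 days of screening. Screening may be shorter than that, or longer where abbreviated rescreening is used (Protocol 4.6.2.1).

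A reader might infer that pre-dose events will be counted, that the upper figures are the expected bias, or that all of Tables 4-14 are affected alike. The documents support none of these: 5.3.1 may keep most such events out, the background rates are assumptions, and the tables restricted to related events are largely protected.

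The change should still be made. The endpoint is primary, one patient is worth 16.7 to 33.3 points, and the stated rule gives the wrong count whenever a pre-dose AE is captured.

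**What to change.** In SAP 4.2:
- Define a treatment-emergent AE as one with onset, or worsening in severity, at or after the first dose of that course, up to the Day 28 visit. Tying it to the course also settles the case of re-entering patients.
- Base the AE, SAE and AESI tables on this definition, and say so in the shell footnotes.
- List AEs with onset before first dose separately.
- Because SAP 2.3 imputes nothing, state how a partial onset date, or a Day 1 onset without a clock time, is classified.

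Reconcile the Protocol Synopsis, Appendix 1 and SAP 1.2 with Protocol 5.3.1, so that one rule states which pre-dose AEs go on the eCRF.

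The cost is one SAP definition, footnotes and one listing, plus a clarifying edit to the protocol. Treatment start and AE start dates are already in Data Listing 3. No new data are needed and the sample size does not change.
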